## 2. ABBREVIATIONS

Abbreviations pertain to the Statistical Analysis Plan (SAP) only (not the tables, figures and listings [TFLs]).

AE	Adverse event
ALP	Alkaline phosphatase
ALT	Alanine aminotransferase
AUC	Area under the concentration versus time curve
AUC(0-∞)	Area under the concentration versus time curve from time zero to infinity
AUC(0-t last )	Area under the concentration versus time curve from time zero to time t, where t is the last time point with a measurable concentration
%AUC(t last -∞)	Percentage of AUC(0-∞) extrapolated
AUC τ	Area under the concentration versus time curve during one dosing interval
bid	Twice daily
bpm	Beats per minute
BQL	Below the quantifiable lower limit of the assay
CI	Confidence interval
C max	Maximum observed drug concentration
CL/F	Apparent total body clearance of drug calculated after extra-vascular administration
CRF	Case Report Form
CSR	Clinical Study Report
CRU	Clinical Research Unit
CV	Coefficient of variation
EC	Early Clinical
ECG	Electrocardiogram
e.g.	For example (Latin: exempli gratia )
HR	Heart rate
ICH	International Council on Harmonisation
LLOQ	Lower limit of quantification
MedDRA	Medical Dictionary for Regulatory Activities

---

MRE	Magnetic resonance elastography
NA	Not applicable
PK	Pharmacokinetic
SAP	Statistical Analysis Plan
SD	Standard deviation
SOP	Standard Operating Procedure
TBL	Total bilirubin
TFLs	Tables, Figures, and Listings
$t_{1/2}$	Half-life associated with the terminal rate constant ( $\lambda_z$ ) in non-compartmental analysis
$t_{max}$	Time of maximum observed drug concentration
ULN	Upper limit of normal
$V_{ss}/F$	Apparent volume of distribution at steady state after extra-vascular administration
$V_z/F$	Apparent volume of distribution during the terminal phase after extra-vascular administration
WHO	World Health Organization

### **3. INTRODUCTION**

This SAP has been developed after review of the Clinical Study Protocol (final version dated 27 June 2017) and Protocol Amendment (a) (final version dated 20 October 2017) .

This SAP describes the planned analysis of the safety, tolerability and pharmacokinetic (PK) data from this study. A detailed description of the planned TFLs to be presented in the clinical study report (CSR) is provided in the accompanying TFL shell document.

The intent of this document is to provide guidance for the statistical and PK analyses of data. In general, the analyses are based on information from the protocol, unless they have been modified by agreement between Eli Lilly and Company and Covance Early Clinical (EC) Biometrics. A limited amount of information concerning this study (e.g., objectives, study design) is given to help the reader's interpretation. This SAP must be signed off prior to first subject administration for this study. When the SAP and TFL shells are agreed upon and finalized, they will serve as the template for this study's CSR.

This SAP supersedes the statistical considerations identified in the protocol; where considerations are substantially different, they will be so identified. If additional analyses are required to supplement the planned analyses described in this SAP, they may be performed and will be identified in the CSR. Any substantial deviations from this SAP will be agreed upon between Eli Lilly and Company and Covance EC Biometrics and identified in the CSR. Any minor deviations from the TFLs may not be documented in the CSR.

This SAP is written with consideration of the recommendations outlined in the International Council on Harmonisation (ICH) E9 Guideline entitled Guidance for Industry: Statistical Principles for Clinical Trials and the ICH E3 Guideline entitled Guidance for Industry: Structure and Content of Clinical Study Reports.

### **4. STUDY OBJECTIVES**

#### **4.1 Primary Objective**

The primary objective of this study is to evaluate the effects of propranolol alone and in combination with lasmiditan on heart rate (HR).

#### **4.2 Secondary Objectives**

The secondary objectives of this study are:

- To evaluate the effects of propranolol alone and in combination with lasmiditan on blood pressure and PR interval.
- To explore the tolerability of a single dose of lasmiditan alone or in combination with propranolol.
- To evaluate the PK of lasmiditan alone and in combination with propranolol.
- To evaluate the PK of propranolol alone and in combination with lasmiditan.

#### **4.3 Exploratory Objectives**

The exploratory objectives of this study are:

- To evaluate the effects of lasmiditan alone and in combination with propranolol on orthostatic changes in blood pressure and pulse rate.
- To evaluate the PK of the metabolites M8, M7, and M18 in healthy subjects following a single 200-mg oral dose of lasmiditan alone and in combination with propranolol.

### **5. STUDY DESIGN**

This is an open-label, fixed-sequence study in healthy subjects to assess the cardiovascular effects of coadministration of lasmiditan with propranolol.

#### Screening Period:

All subjects will participate in a screening visit up to 28 days prior to the first lasmiditan dose.

#### Dosing Period:

Subjects will be admitted to the clinical research unit (CRU) on Day -2. On Day 1, subjects will receive a single dose of 200 mg lasmiditan, then receive propranolol (immediate release formulation; half-life approximately 3 to 6 hours) 80 mg twice daily (bid) on Days 4 through 10 and a single dose of 200 mg lasmiditan coadministered with propranolol on Day 9. Subjects will reside in the CRU from Day -2 until Day 11 when they may be discharged from the CRU following completion of all study procedures, at the investigator's discretion.

Study governance considerations are described in detail in Appendix 3 of the protocol.

Blood samples will be collected predose and up to 48 hours postdose on Days 1 and 9 for the measurement of plasma concentrations of lasmiditan and its metabolites. Blood samples will also be collected predose and up to 12 hours postdose on Days 8 and 9 for the measurement of plasma concentrations of propranolol.

[figure not shown]
Safety assessments performed during the study will include adverse events (AEs), clinical laboratory evaluations, vital signs measurements, 12-lead ECGs, and physical examinations.

Cardiovascular effects will be assessed by Holter ambulatory monitoring and replicate measurements of blood pressure at predose, and for 12 hours postdose on Days -1, 1, 8, and 9.

#### Follow-up Period

Subjects will attend a follow-up visit approximately 7 days after the last dose.

Figure 1 illustrates the study design.

**Figure 1. Illustration of study design for Protocol H8H-MC-LAHD**

## 6. TREATMENTS

The treatment sequence to be administered to all subjects is: 200 mg lasmiditan (Day 1); 80 mg propranolol bid (Day 4 to Day 10); 200 mg lasmiditan + 80 mg propranolol (Day 9).

The following is a list of the study treatments that will be used in the TFLs.

Study Treatment Name	Treatment order in TFL
200 mg lasmiditan	1
80 mg propranolol bid	2
80 mg propranolol bid + 200 mg lasmiditan	3

## 7. SAMPLE SIZE JUSTIFICATION

Up to 44 subjects may be enrolled to ensure 36 subjects complete the study. Assuming a standard deviation for the change in HR of 10.9 (based on previous studies [H8H-MC-CD-LAHO and H8H-CD-LAHJ]), this will result in a 90% probability that the half-width of the 90% confidence interval (CI) about the mean within-subject change is no larger than 5 beats per minute (bpm). Subjects who are randomized but do not complete the study may be replaced to ensure that enough subjects complete the study.

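### The sample-size statement does not follow from its inputs: with an SD of the heart-rate change of 10.9 and 36 completers, the probability of a 90% CI half-width of 5 bpm or less is over 99.99%, not 90%

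*SAP*

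**What the plan says.** SAP Section 7 begins "Up to 44 subjects may be enrolled to ensure 36 subjects complete the study". It continues "Assuming a standard deviation for the change in HR of 10.9", citing two previous studies as the source, and concludes that there is a "90% probability that the half-width of the 90% confidence interval (CI) about the mean within-subject change is no larger than 5" bpm. It gives no second SD, no correlation between measurements and no conversion from one kind of SD to another.

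The design is a single group in a fixed sequence (Section 5: "This is an open-label, fixed-sequence study in healthy subjects"). Section 9.4.2 compares Day 9 (combination) with Day 8 (propranolol alone) in a mixed model with a fixed treatment effect and a random subject effect, and reports a 90% CI for the mean difference. The same model is used for Day 9 against Day 1. With complete pairs, either comparison is a paired t interval on n − 1 degrees of freedom.

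**The concern.** The SD is described as that of a change, and the interval is for the mean of a within-subject change. The natural reading puts 10.9 straight into the paired interval, and the result is then far tighter than the plan claims.

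This is the only precision the SAP states, and it concerns the primary objective. Section 9.4.2 sets no equivalence margin or formal test for heart rate, so the CI width is the whole stated reason for the trial's size. A reader who trusts the label expects a half-width near 3.1 bpm; if 10.9 is a within-subject SD, the half-width will be near 4.3 bpm. Anyone who reuses 10.9 as an SD of change to plan another study would then understate the variance by half. If the label is literally right, the plan asks for 15 more healthy completers (36 − 21) than its own target needs.

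**Working it through.** **Inputs (SAP Section 7).** n = 36 completers; SD labelled as that of the change = 10.9 bpm; two-sided 90% CI; half-width limit h = 5 bpm; stated probability 90%.

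**Formula.** The half-width is t(0.95, n−1) × S / √n, where S is the sample SD of the change. Since (n−1)S²/SD² is chi-squared on n−1 df,

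P(half-width ≤ h) = P( χ²(n−1) ≤ (n−1) × n × h² / (t² × SD²) ).

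For n = 36, t(0.95, 35) = 1.6896, and the numerator is 35 × 36 × 25 = 31,500.

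**Step 1: as labelled, SD of the change = 10.9.**
- Threshold: 31,500 / (1.6896² × 10.9²) ≈ 92.9 on 35 df, so P = 0.9999996.
- Half-width when S equals 10.9: 1.6896 × 10.9 / 6 = 3.07 bpm.
- Half-width met with 90% probability: 3.52 bpm.
- Smallest n that reaches 90% for 5 bpm: 21 (92.5%); n = 20 gives 88.9%.

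The stated 90% is not reproduced.

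**Step 2: other conventions, keeping 10.9 as the SD of the change.**

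| Variant | P(half-width ≤ 5) |
|---|---|
| Normal quantile in place of t | > 99.99% |
| 95% CI | 99.8% |
| 98% CI | 87.2% |
| 99% CI | 56.6% |
| One-sided 90% limit | about 100% |
| Full width of 5 in place of half-width | 6.4% |
| n = 44 | > 99.99% |
| Conditional on the interval covering the true mean | > 99.99% |
| Two independent groups of 18 / of 36 | 6.6% / 97.7% |

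None comes within 2 points of 90%. The nearest, a 98% CI, is not the interval the plan names.

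**Step 3: 10.9 as the within-subject (residual) SD.** The difference of two measurements then has SD 10.9 × √2 = 15.41.
- Threshold: 31,500 / (1.6896² × 15.41²) ≈ 46.4 on 35 df, so P = 90.6%.
- Half-width when S equals 15.41: 1.6896 × 15.41 / 6 = 4.34 bpm.
- Half-width met with 90% probability: 4.98 bpm.
- n = 35 gives 87.9%, so 36 is exactly the smallest n that reaches 90%.

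**Step 4: solving backwards.** Fixing n = 36, 5 bpm and 90% requires an SD of the change of 15.48, and 15.48 / √2 = 10.94. That agrees closely with 10.9.

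**The case against.** The arithmetic is not in dispute; the diagnosis can be challenged. Section 9.1 defines change from baseline for each subject, and Section 9.5.7 applies a predose baseline to the Holter heart rate. So 10.9 might be the SD of change from baseline under one treatment in the earlier studies, while the interval concerns the difference between two such changes. If those changes were uncorrelated, the SD of the difference would again be 10.9 × √2 = 15.4. The label would then be accurate, and what is missing would be the conversion.

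This possibility stands as an alternative origin of the √2, but it does not rescue the sentence. The SAP states neither the conversion nor a zero correlation, and the result depends on that correlation: with correlation ρ the SD of the difference is 10.9 × √(2(1 − ρ)), so ρ = 0.5 returns it to 10.9 and the probability to over 99.99%. The model in Section 9.4.2 also has no baseline subtraction. On this reading too, 10.9 is not the SD of the quantity whose CI is being sized.

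It is also fair to say that the practical harm is limited. The exact match at n = 36 points to a wording error and makes an oversized trial the less likely explanation. The final analysis estimates its own variance, and no test, decision threshold or interim look uses 10.9.

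**Conclusion.** The point holds. As labelled, the inputs in Section 7 give a probability above 99.99% where the plan states 90%. The SD of the change that the plan's own figures imply is about 15.4 to 15.5, larger than the stated SD by a factor of about 1.41. The half-width to expect is 3.07 bpm on one reading and 4.34 bpm on the other, and the number of completers needed is 21 or 36.

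The calculation assumes complete pairs from 36 subjects and normally distributed changes. The failure to reproduce is a matter of arithmetic. The explanation, a within-subject SD labelled as the SD of the change, is an inference from the close numerical match, because the source studies are not available here. The trial is not too small: 36 completers meet the 5 bpm target with at least 90% probability on either reading.

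**What to change.** Check 10.9 against the two studies cited in Section 7, then correct the sentence in one of these ways:

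- **If it is the within-subject SD:** say so, add that the SD of the within-subject change is 15.4 bpm, and keep 36 completers, 90% and 5 bpm.
- **If it is the SD of the change being analysed:** keep the label and 36 completers, and restate the half-width met with 90% probability as about 3.5 bpm.
- **If it is the SD of a one-treatment change from baseline:** state that, give the assumed correlation, and report the resulting SD of the between-day difference.

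In each case, name the contrast that the SD refers to (Day 9 against Day 8, or Day 9 against Day 1). The cost is one sentence in SAP Section 7, and the same edit in the protocol if it carries the same wording; the protocol was not available for this check. Neither enrolment nor the analysis changes.

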## 8. DEFINITION OF ANALYSIS POPULATIONS

The “Safety” population will consist of all enrolled subjects, whether or not they completed all protocol requirements.

The “Pharmacokinetic” population will consist of all subjects who received at least one dose of lasmiditan or propranolol and have evaluable PK data.

The “Cardiovascular” population will consist of all subjects who had the relevant test and reference treatment measurements.

All protocol deviations that occur during the study will be considered for their severity/impact and will be taken into consideration when subjects are assigned to analysis populations.

## **9. STATISTICAL METHODOLOGY**

### **9.1 General**

Data listings will be provided for all data that are databased. Summary statistics and statistical analysis will only be presented for data where detailed in this SAP. For continuous data, summary statistics will include the arithmetic mean, arithmetic standard deviation (SD), median, min, max and N; for log-normal data (e.g. the PK parameters: area under the concentration versus time curve [AUCs] and maximum observed drug concentration [ $C_{max}$ ]) the geometric mean and geometric coefficient of variation (CV%) will also be presented. For categorical data, frequency count and percentages will be presented. Data listings will be provided for all subjects up to the point of withdrawal, with any subjects excluded from the relevant population highlighted. Summary statistics and statistical analyses will generally only be performed for subjects included in the relevant analysis population. For the calculation of summary statistics and statistical analysis, unrounded data will be used.

Mean change from baseline is the mean of all individual subjects' change from baseline values. Each individual change from baseline will be calculated by subtracting the individual subject's baseline value from the value at the timepoint. The individual subject's change from baseline values will be used to calculate the mean change from baseline using a SAS procedure such as Proc Univariate.

Data analysis will be performed using SAS® Version 9.4 or greater.

### **9.2 Demographics and Subject Disposition**

Subject disposition will be listed. The demographic variables age, sex, race, ethnicity, country of enrolment, site ID, body weight, height and body mass index will be summarized and listed.

### **9.3 Pharmacokinetic Assessment**

#### **9.3.1 Pharmacokinetic Analysis**

Pharmacokinetic parameter estimates will be determined using non-compartmental procedures in validated software program (Phoenix WinNonlin Version 6.4 or later).

Plasma concentrations of lasmiditan (LY573144) and its metabolites will be used to determine the following PK parameters, when possible:

Parameter	Units	Definition
$C_{\max}$	ng/mL	maximum observed drug concentration
$t_{\max}$	h	time of maximum observed drug concentration
$AUC(0-\infty)$	ng.h/mL	area under the concentration versus time curve from time zero to infinity
$AUC(0-t_{\text{last}})$	ng.h/mL	area under the concentration versus time curve from time zero to time $t$ , where $t$ is the last time point with a measurable concentration
% $AUC(t_{\text{last}}-\infty)$	%	percentage of $AUC(0-\infty)$ extrapolated
$t_{\frac{1}{2}}$	h	half-life associated with the terminal rate constant ( $\lambda_z$ ) in non-compartmental analysis
CL/F	L/h	apparent total body clearance of drug calculated after extra-vascular administration (LY573144 only)
$V_z/F$	L	apparent volume of distribution during the terminal phase after extra-vascular administration (LY573144 only)
$V_{ss}/F$	L	apparent volume of distribution at steady state after extra-vascular administration (LY573144 only)
MR		Metabolic ratio a

a no molar correction will be applied since the metabolites are very similar in molecular weight and within 5% of the molecular weight for lasmiditan.

Plasma concentrations of propranolol will be used to determine the following PK parameters, when possible:

Parameter	Units	Definition
$C_{\max}$	ng/mL	maximum observed drug concentration
$t_{\max}$	h	time of maximum observed drug concentration
$AUC_{\tau}$	ng.h/mL	area under the concentration versus time curve during one dosing interval
CL/F	L/h	apparent total body clearance of drug calculated after extra-vascular administration

Additional PK parameters may be calculated, as appropriate. The software and version used for the final analyses will be specified in the clinical study report. Any exceptions or special handling of data will be clearly documented within the final study report.

Formatting of tables, figures and abbreviations will follow the Eli Lilly Global PK/PD/TS Tool: NON-COMPARTMENTAL PHARMACOKINETIC STYLE GUIDE. The version of the tool effective at the time of PK analysis will be followed.

## General PK Parameter Rules

- Actual sampling times will be used in the final analyses of individual PK parameters, except for non-bolus predose sampling times which will be set to zero. For non-bolus, multiple dose profiles, the predose time will be set to zero unless a time deviation falls outside of the protocol blood collection time window which is considered to impact PK parameter derivation.
- $C_{\max}$  and  $t_{\max}$  will be reported from observed values. If  $C_{\max}$  occurs at more than one time point,  $t_{\max}$  will be assigned to the first occurrence of  $C_{\max}$ .
- AUC parameters will be calculated using a combination of the linear and logarithmic trapezoidal methods (linear-log trapezoidal rule). The linear trapezoidal method will be applied up to  $t_{\max}$  and then the logarithmic trapezoidal method will be used after  $t_{\max}$ . The minimum requirement for the calculation of AUC will be the inclusion of at least three consecutive plasma concentrations above the lower limit of quantification (LLOQ), with at least one of these concentrations following  $C_{\max}$ . AUC(0-∞) values where the percentage of the total area extrapolated is more than 20% will be flagged. Any AUC(0-∞) value excluded from summary statistics will be noted in the footnote of the summary table.
- Half-life ( $t_{1/2}$ ) will be calculated, when appropriate, based on the apparent terminal log-linear portion of the concentration-time curve. The start of the terminal elimination phase for each subject will be defined by visual inspection and generally will be the first point at which there is no systematic deviation from the log-linear decline in plasma concentrations. Half-life will only be calculated when a reliable estimate for this parameter can be obtained comprising of at least 3 data points. If  $t_{1/2}$  is estimated over a time window of less than 2 half-lives, the values will be flagged in the data listings. Any  $t_{1/2}$  value excluded from summary statistics will be documented in the footnote of the summary table.
- A uniform weighting scheme will be used in the regression analysis of the terminal log-linear portion of the concentration-time curve.
- The parameters based on predicted  $C_{\text{last}}$  will be reported.

## Individual PK Parameter Rules

- Only quantifiable concentrations will be used to calculate PK parameters with the exception of special handling of certain concentrations reported below the lower limit of quantitation (BQL). Plasma concentrations reported as BQL will be set to a value of zero when all of the following conditions are met:
  - The compound is non-endogenous.
  - The samples are from the initial dose period for a subject or from a subsequent dose period following a suitable wash-out period.
  - The time points occur before the first quantifiable concentration.

- All other BQL concentrations that do not meet the above criteria will be set to missing.
- Also, where two or more consecutive concentrations are BQL towards the end of a profile, the profile will be deemed to have terminated and therefore any further quantifiable concentrations will be set to missing for the calculation of the PK parameters unless it is considered to be a true characteristic of the profile of the drug.

### **Individual Concentration vs. Time Profiles**

- Individual concentrations will be plotted utilizing actual sampling times.
- The terminal point selections will be indicated on a semi-logarithmic plot.

### **Average Concentration vs. Time Profiles**

- The average concentration profiles will be graphed using scheduled (nominal) sampling times.
- The average concentration profiles will be graphed using arithmetic average concentrations.
- The predose average concentration for single-dose data from non-endogenous compounds will be set to zero. Otherwise, only quantifiable concentrations will be used to calculate average concentrations.
- Concentrations at a sampling time exceeding the sampling time window specified in the protocol, or  $\pm 10\%$ , will be excluded from the average concentration profiles.
- Concentrations excluded from the mean calculation will be documented in the final study report.
- A concentration average will be plotted for a given sampling time only if 2/3 of the individual data at the time point have quantifiable measurements that are within the sampling time window specified in the protocol or  $\pm X\%$ . An average concentration estimated with less than 2/3 but more than 3 data points may be displayed on the mean concentration plot if determined to be appropriate and will be documented within the final study report.

